9.3.2 Virus Inoculation (Day 0)

All baseline procedures and tests will be performed prior to challenge virus administration. Once it has been determined that the participant still meets eligibility criteria for the study and that he/she is comfortable in the unit, administration of the challenge virus will proceed at a dose of 10^7 TCID₅₀ on Day 0. Once the influenza challenge virus has been administered, participants will remain hospitalized in isolation on the unit for a minimum of 8 additional days and will be discharged only after they meet the discharge criteria described below.

9.3.3 Day 1 through 7

While admitted to the Quarantine Unit, participants will remain in isolation in their room. Participants will undergo study procedures which will be conducted as detailed on the Time and Events table 9.2

Participants will be discharged when they meet the following discharge criteria: 2 consecutive negative morning nasal swabs (that occur on 2 different but consecutive days) for influenza A, are afebrile, show no signs of significant influenza symptoms, and are clinically and hemodynamically stable. It is expected that participants will shed virus for 3 to 5 days post inoculation; therefore, we expect most participants to have 2 consecutive negative nasopharyngeal swabs by Day 7 of the study.

The FLU-PRO questionnaires will be completed in paper form.

9.3.4 Discharge

Starting from Day 7 subjects will be discharged from the Quarantine Unit if the morning nasopharyngeal swab sample is negative (on two separate but consecutive days) for Challenge Virus. If the test is positive or the subject remains symptomatic, the subject will be asked to remain in the Quarantine Unit for further observation at the discretion of the PI.

9.3.5 Day 8 through 15 (if required)

All subjects will complete diary card up to Day 15 while at home.

All subjects remaining in quarantine unit will follow assessments as detailed in the T&E

9.4 Visit 5 & 6 - Follow-up phase

All participants will be followed for a minimum of 8 weeks after completing the inpatient portion of the study. Any participant who experiences complications due to challenge virus administration or study drug will be followed until resolution of such complications or appropriate referral to the necessary medical care has been made.

Follow-up visits will take place on Day 35 (+/-3 days) and Day 63 (+/-5) days or more often if deemed medically necessary; the procedures/evaluations to be conducted at these visits are shown in T&E schedule. Day 63 will be the final study visit unless the participant requires additional follow-up of study-related complications.

Participants will be asked to report to the study team if any close contacts become ill with an influenza-like illness. If a close contact becomes ill with an influenza-like illness during the follow-up period, the participant will be asked to contact that individual and have them contact the hVIVO study team. The possibly infected person will be asked to come to the hVIVO facility for an assessment.

9.4.1 Lost to follow-up

In the event that a subject does not return for the final follow-up visit post-Viral Challenge; the Investigator will make every reasonable effort to contact the subject to review all AEs. In the event that a subject drops out of the study at any time, the reason for discontinuation, if known, must be fully documented in the source data. The site personnel will document the AEs and any other assessments and will make every effort to complete all required end of study assessments.

9.5 End of trial

The end of the trial is defined as the last subject's last scheduled visit (LSLV). If an additional visit is required after the last scheduled visit, this will be at the PI's discretion, for example, repeat spirometry or laboratory tests. Such discretionary follow-up visits will not be considered part of the trial data unless they represent follow-up and closure on an AE or SAE identified during the trial period.

AEs that are unresolved at the follow-up visit may necessitate further follow-up visits if required.

9.5.1 End of Trial Report

It is the Sponsor's responsibility to send the End of Trial Report to the Medicines and Healthcare products Regulatory Agency (MHRA) and Research Ethics Committee (REC) within 1 year of the end of the trial.

10 RANDOMISATION AND BLINDING

123 subjects will be randomised 1:1:1 to:

- Group 1: adjuvanted placebo on Day -43 and on Day -22
- Group 2: 500 mcg adjuvanted FLU-v vaccine on Day -43 and 1 dose of adjuvanted placebo on Day -22
- Group 3: 500 mcg adjuvanted FLU-v vaccine on Day -43 and on Day -22

10.1 Route of administration, dosage, dose regimen and treatment period

The route of administration was chosen based on the animal data and on the adjuvant manufacturer. The mechanism of action of oil adjuvant-based vaccines includes the formation of a depot at the injection site, enabling the slow release of the antigen and the stimulation of antibody-producing plasma cells. These formulations promote antigen uptake by APCs. Formulated antigens are concentrated and protected against degradation, while phagocytosis is stimulated by different ligand/receptor interactions. Subcutaneous injection is ideal for that.

The dosage selection is supported by animal data and also previous clinical trial showing that 500ug was better than 250ug. In clinical trials we have only given a single dose of FLU-v but animal data (presented in IB), shows that a second dose boosts the response. The two doses are given 3 weeks apart because that is the necessary length of time required for the immune system to mature the response to the antigen administered.

10.2 Randomisation for the study

Potential subjects will be assigned a unique hVIVO subject number that will be used to identify them prior to entry to the study and during the study until the point of randomisation. Once a subject is randomised they will be allocated a randomisation number.

Randomisation will occur on Day -43 Randomisation numbers will be assigned sequentially in ascending order, and once assigned, a randomisation number shall not be reassigned. The study site will keep a log of the randomisation number assigned to each subject.

The assigned randomisation number and the randomisation schedule will determine which arm the participant will be in. Treatments will be assigned in a ratio of 1:1:1.

Randomisation numbers will follow a 3 digit format e.g., 101-1NN. A copy of the randomisation code list will be sent to the unblinded pharmacist preparing the vaccines, so that vaccine or placebo doses can be prepared for each subject as appropriate.

A designated unblinded statistician will be responsible for the computer generated randomisation schedule. Sealed copies of the randomisation code will be stored in a secure place. Following database lock, on receipt of authorisation from the Sponsor, a copy of the randomisation code list will be sent to the Study Statistician to conduct study unblinding.

10.3 Blinding

The PI will be provided with a tamper evident sealed envelope containing details of the treatment for each subject. All opened and unopened envelopes will be collected after the end of the subject's participation in the study.

With the exception of the manufacturer's pharmacy department, the independent statistician preparing the randomisation code list, the unblinded Clinical Research Associate (CRA) and the Quality Assurance (QA) auditors where necessary, the Investigator and all other clinical and non-clinical staff, including the Study Statistician, data management staff, and subjects, will remain blinded to the treatment allocation until after the database has been locked and approval for study unblinding has been given. The confidentiality of the randomisation code list and study blinding will be maintained.

10.4 Unblinding

Randomisation codes will be provided to the Pharmacist or designee at the start of the study. Individual emergency code break envelopes will be provided to hVIVO should it be necessary to break the blind for a subject. The Investigator will ensure there is an appropriate procedure in place to allow access to the code break envelopes in case of an emergency arising during the quarantine period, as per hVIVO's or HMR's standard operating procedures (SOPs). In the event of such an 'emergency', the relevant medical decision on the further care of a subject would depend on the actual identity of the study treatment that the subject received.

The emergency code break envelopes will contain information stating either 'This subject was on active drug' or 'This subject was on placebo'. Any premature code breaking will be explained and justified by the Investigator and hVIVO, and the Sponsor must be promptly informed. If possible, the Sponsor should be consulted before the code is broken.

When the code break envelope is opened, the Investigator must note the date, time, reason for unblinding and personnel details and record this information according to hVIVO SOPs. The Investigator must also immediately notify the Sponsor's Medical Expert (SME) that the code has been broken.

Even if the code is broken, blood samples for safety, efficacy, and other parameters assessments will continue to be drawn for the remainder of the planned study period following the last dose as long as doing so will not compromise subject welfare.

In the event of unblinding, the subject will still be followed up until resolution of any AEs.

If a subject's randomisation code is unblinded by the PI or study site personnel, the subject must be withdrawn from the study and followed up as appropriate. If the Sponsor breaks the code for safety reporting purposes, the subject may remain in the study.

11 CHALLENGE VIRUS

11.1 Description

Using reverse genetics, an investigational live Influenza A 2009 H1N1 human challenge virus similar to the wild-type strain A/Ca/04/2009 was manufactured in certified Vero cells under Good Manufacturing Practice (GMP) conditions by Charles River Laboratories in Malvern, PA from a seed stock produced by [name] and his laboratory team in the Viral Pathogenesis and Evolution Section of the LID. It will be vialled at a maximum dose level of 10^{12} TCID₅₀. This virus has been demonstrated to be sensitive to standard FDA-approved neuraminidase inhibitors such as oseltamivir and zanamivir. Similar to current seasonal H3N2 and all 2009 H1N1 pandemic viruses, it is resistant to the adamantanes.

11.2 Supply and accountability

hVIVO is obliged to establish a system for control of Challenge Virus, to ensure all supplies are received by a responsible person, and all deliveries and returns are documented and signed for.

The PI will maintain accurate records of receipt and condition of all Challenge Virus inoculum stock, including dates of receipt, and details and dates of the quantities dispensed and used in the study. Any departures from the protocol-dispensing regimen will be fully documented.

Challenge inoculum accountability records will be available for verification by the Study Monitor.

11.3 Storage

The Influenza A 2009 H1N1 human challenge virus will be stored at -60°C to -90°C in single-use vials. Multiple doses of virus may be prepared from the same vial after it is opened. Once opened, each vial will be discarded appropriately after use. Preparation and administration procedures will be documented in a laboratory analytical plan.

11.4 Preparation and administration

Challenge virus preparation and administration procedures will be documented in a laboratory analytical plan. This will be performed by trained personnel in the hVIVO laboratory.

12 INVESTIGATIONAL MEDICINAL PRODUCT

12.1 Description

12.1.1 FLU-v

FLU-v is a lyophilised product composed of four short peptidic active pharmaceutical ingredients (APIs) (FLU-5, FLU-7, FLU-8N and FLU-10). The APIs are manufactured by fluorenylmethoxycarbonyl (Fmoc) chemistry before reconstituting them in 50% acetic acid and mixed to prepare an equimolar solution of the four peptides. Glass vials are then filled with the solution under sterile conditions. Water and acetic acid are removed from the preparation by lyophilisation. The end product is a white to off white lyophilised solid that will need reconstitution prior administration by injection. It is subcutaneously administered and supplied in single-use vials as a dose of 500 micrograms suspended in 0.5ml volume of water and adjuvant. The intended application of the investigational medicinal product is as a prophylactic vaccine to prevent influenza virus infection by inducing an enhanced immune response.

12.1.2 Placebo

The placebo is adjuvant (Montanide ISA-51)

12.2 Supply and accountability

hVIVO external pharmacy vendor will only receive supplies of FLU-v and adjuvant once it has Qualified Person (QP) sign off by the GMP Pharmacy provider, and the IMP has been verified ready for dispatch. All IMP supplies will be used only for this protocol and for no other purpose.

Once received at hVIVO external pharmacy vendor, will perform stock level accountability. Vaccine accountability will be controlled by hVIVO external vendor and monitored by the Study Monitor throughout the study and at study closeout.

The Investigator will ensure that a responsible person receives all supplies, all deliveries and returns are documented and signed for, and the condition of the vaccine is monitored. Accurate records will be kept of when and how much vaccine is dispensed and used in the study. Any reasons for departure from the dispensing protocol will also be recorded.

FLU-v or placebo will be supplied only to subjects participating in the study. It must not be relabelled or reassigned for use by other subjects.

Accountability records will be available for verification by the Study Monitor at each monitoring visit. At the completion of the study, there will be a final reconciliation of all IMP.

12.3 Packing and labelling

FLU-v-004 and placebo will be packed under the responsibility of the Sponsor.

FLU-v-004 and placebo will be packed per subject according the randomisation list, assuring double-blindness for the FLU-v-004 versus placebo part of the study. All supplies will be packaged and received in accordance with Annex 13 of Eudralex volume 4 and the current version of the 'Rules and Guidance for Pharmaceutical Manufacturers and Distributors'³⁰. Blinding, randomisation, and labelling will be performed at a GMP Pharmacy.

A release document signed by a legally authorised QP will be kept in the Trial Master File to document labelling and dispensing of the IMP to the subject. All documents required to perform GMP activities will be supplied as per the Technical Agreement.

Labelling and packing of study medication will be in accordance with current regulatory standards.^{3,31-33}

No medication can be relabelled without prior approval from PepTcell (t/a SEEK).

Storage

FLU-v vials will be stored at -15 to -25°C. The determination of the shelf life for the IMP is on-going. Stability studies of previous batches indicate that it should remain stable for 2 years when stored at -20°C.

The vials of water for injection, Montanide ISA-51 should be stored at room temperature.

None of the materials can be dispensed beyond the expiry date.

Provision must be in place to store the IMP within the permitted temperature range. Temperature must be monitored regularly, ideally using a continuing electronic monitoring system (24/7) is expected. However, it is acceptable to use a well-maintained system of max min thermometer recording at least once per working day. Diligence is expected in checking that at the time of dispensing, the IMP has always been stored in the permitted range.

Whichever system is adopted the equipment must be regularly calibrated and a certificate of recalibration be available to the Sponsor / monitor to review.

Temperature logs should be maintained at all times and be available for inspection by the monitoring team, when requested at monitoring visits.

Should there be a deviation in the storage temperature of the IMP, it must be immediately quarantined. The deviation must be recorded on the Temperature Deviation Form. The Investigator should be immediately contacted and eventual IMP already dispensed recalled. Subject safety should be managed according to GCP.

12.4 Administration

The IMP will be administered in accordance with the study Pharmacy manual.

The investigator or delegate will be responsible for the administration of the vaccine to subjects enrolled into the study according to the procedures in the Pharmacy Manual.

Precautions:

Study vaccines should not be administered to individuals with known hypersensitivity to any component of the vaccines.

Any temperature $> 38.0^{\circ}\text{C}$ or active infection is reason for delaying vaccination or according to eligibility and other criteria in section 7.4.2.

Standard immunization practices should be observed and care taken to administer the injection avoiding intravascular injection.

Subjects will be observed for 60 minutes after each injection for any immediate reactions. All subjects will be instructed to complete an adverse event diary card for 21 days for local symptoms (i.e., ecchymosis, erythema, induration, swelling and pain at the injection site) and systemic symptoms (i.e., chills, malaise, myalgia, arthralgia, nausea, headache, sweating, and fatigue) after each injection. Additional monitoring may be required for clinically significant reported events.

Appropriate medical treatment and supervision should be readily available in the case of rare anaphylactic reactions following administration of the study vaccine. Adrenaline 1:1000, Chlorpheniramine and Hydrocortisone, as per the Resuscitation Council (UK) should be readily available in case of any anaphylactic reactions.

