The majority of TEAEs were reported in the system organ class of general disorders and administration site conditions; 15 TEAEs reported by subjects receiving 250 µg FLU-v without adjuvant, 29 TEAEs reported by subjects receiving 250 µg FLU-v with adjuvant, 15 TEAEs reported by subjects receiving 500 µg FLU-v without adjuvant and 34 TEAEs reported by subject receiving 500 µg FLU-v with adjuvant. Injection site pain was the most frequently reported TEAE and subjects receiving FLU-v with adjuvant reported more events of injection site pain (approximately 2-fold difference) than subjects receiving FLU-v without adjuvant. Within this system organ class, injection site pruritus (6 events), injection site swelling (6 events) and pyrexia (1 event) were only reported by subjects receiving adjuvant.

Adverse events of headache, malaise, fatigue, myalgia, nausea, vomiting diarrhoea, chills fever and other (as reported by the subject) were assessed for systemic tolerability. Neither vomiting nor chills were reported by subjects during the trial. The most commonly reported TEAEs by subjects receiving FLU-v were headache (11 events), fatigue (9 events), malaise

(7 events), myalgia (7 events) and nausea (4 events). One event each of diarrhoea and pyrexia were reported.

Assessment of local tolerability (itching, pain and tenderness) indicated that the majority of reactions were reported at the 0.08 h (5 minute) post dose time point. Most reactions were reported as mild and there were no reported severe reactions.

There were no clinically significant findings in either the individual or mean laboratory measurements, vital signs or ECG measurements.

In conclusion, no safety or tolerability concerns were identified at the doses administered (250 μ g and 500 μ g FLU-v) to the subjects in the study. No safety or tolerability concerns were identified following administration of the adjuvant to the subjects in the study.

The FLU-v vaccine candidate was demonstrated to be immunogenic in humans, as measured by ex vivo INF- γ production.

Phase Ib study (FLU-v-002)

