13.2.3 Adverse events diary cards (Diary report cards)

To look at expected (solicited) local and systemic signs of reactogenicity, 2 AE diary cards will be issued to all study subjects. The cards will need to be completed by the subjects from Day -43 and returned on D-22 and D-2 or D-1. In the event of missing diary card data, the physician will review the AE diary cards in retrospect, and complete the information as accurately as

possible by asking the subject about any symptoms during the missing day. No protocol deviation will be recorded for the missing diary card data.

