Mucocutaneous	erythema; pruritus	diffuse, maculo papular rash, dry desquamation	vesiculation or moist desquamation or ulceration	exfoliative dermatitis, mucous membrane involvement or erythema, multiforme or suspected Stevens-Johnson or necrosis requiring surgery
Induration	< 15 mm	15 - 30 mm	> 30 mm	
Erythema	< 15 mm	15 - 30 mm	> 30 mm	
Edema	< 15 mm	15 - 30 mm	> 30 mm	
Rash at Injection Site	< 15 mm	15 - 30 mm	> 30 mm	
Pruritus	slight itching at injection site	moderate itching at injection extremity	itching over entire body	
SYSTEMIC				
Allergic Reaction	pruritus without rash	localized urticaria	generalized urticaria; angioedema	anaphylaxis
Headache	mild, no treatment required	transient, moderate; treatment required	severe; responds to initial narcotic therapy	intractable; requires repeated narcotic therapy
Fever: oral	37.7 - 38.5 C or 100.0 - 101.5 F	38.6 - 39.5 C or 101.6 - 102.9 F	39.6 - 40.5 C or 103 - 105 F	> 40 C or > 105 F
Fatigue	normal activity reduced < 48 hours	normal activity decreased 25 - 50% > 48 hours	normal activity decreased > 50% can't work	unable to care for self

For cholesterol and LDL cholesterol, the following severity gradings should be applied:

Cholesterol (fasting)

Adult \geq 18 years

Grade 1: 200 - 239 mg/dL or 5.18 - 6.19 mmol/L

Grade 2: 240 - 300 mg/dL or 6.20 - 7.77 mmol/L

Grade 3: > 300 mg/dL or > 7.77 mmol/L

Grade 4: NA

LDL cholesterol (fasting)

Adult \geq 18 years

Grade 1: 130 - 159 mg/dL or 3.37 - 4.12 mmol/L

Grade 2: 160 - 190 mg/dL or 4.13 - 4.90 mmol/L

Grade 3: \geq 191 mg/dL or \geq 4.91 mmol/L

Grade 4: NA

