- Comparison of each treatment group to placebo of the proportion of asymptomatic infected subjects defined as subjects with symptom score of zero (PAI) from Day 1 post-inoculation time-point through the expected end of quarantine (Day 7) with at least one positive result for viral shedding (RT-qPCR) in any of the quarantine days from the evening of Day 1 post-inoculation.
- Summary of Adverse Events from the Post-Vaccination Diary Card
 - The number of subjects who self-reported at least once any of the adverse events listed in the Post-Vaccination Diary Card during the 21 days following first vaccination and 21 days following second vaccination. Data will be presented for each treatment group by event and according to severity (mild, moderate, severe). The number of subjects in each treatment group with no self-reported events will also be presented.

The statistical software to be used for the analyses will be SAS (version 9.4) and R (version 3.43). The analyses of the secondary binary endpoints will be performed by comparing the rates in each of the FLU-v groups to the placebo group using one-sided Fisher's exact test. For all secondary endpoints, the primary analysis will assume missing data is missing at random so missing data will be ignored.

The analysis of all continuous secondary endpoints will be performed by calculating the median and interquartile range and then performing a one-sided Wilcoxon Rank Sum Test at 0.05 level of significance. These data will be reported as tables and figures as described in sections 8-9 of this document.

Statistical analysis will be performed by a junior statistician at NIAID-NIH and will be reviewed by the senior statistician. In addition, the Senior Clinical and Scientific Leader, will repeat the statistical analysis to validate the results.

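### As Protocol 12.4 describes it, the 21-day diary card does not prompt for injection-site itching or fever, so the diary tables cannot show two reactions that FLU-v-001 reported only in adjuvanted subjects.

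*Protocol*

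**What the plan says.** Protocol 13.2.3 gives the purpose of the card: "To look at expected (solicited) local and systemic signs of reactogenicity, 2 AE diary cards will be issued to all study subjects". Protocol 12.4 gives the period, "All subjects will be instructed to complete an adverse event diary card for 21 days", and the content. The local items are "local symptoms (i.e., ecchymosis, erythema, induration, swelling and pain at the injection site". The systemic items are "systemic symptoms (i.e., chills, malaise, myalgia, arthralgia, nausea, headache, sweating, and fatigue) after each injection". Both lists are introduced by i.e., so they read as complete.

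Protocol 5.2.3.1 describes FLU-v-001. Fever was among the systemic events assessed, and itching was one of three local ones: "Assessment of local tolerability (itching, pain and tenderness) indicated that the majority of reactions were reported" (the sentence goes on to place most of them five minutes after dosing). On general and administration-site events it says that "injection site pruritus (6 events), injection site swelling (6 events) and pyrexia (1 event) were only reported by subjects receiving adjuvant".

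Protocol 9 and 12.1.2 show that all three arms receive adjuvant at both injections, because the placebo is the adjuvant itself.

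Protocol 6.2.1 makes the diary-based incidence of vaccine-related adverse events a secondary endpoint. SAP 5.4 implements it as the number of subjects who "self-reported at least once any of the adverse events listed in the Post-Vaccination Diary Card", by event and severity, in Tables 14.2.2.11.1 and 14.2.2.11.2. The toxicity table in Protocol Appendix 4 already has a fever row and a pruritus row, the latter starting at "slight itching at injection site".

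**The concern.** A solicited-reaction card exists so that expected, short-lived reactions are asked about by name every day. On the sponsor's own earlier data, itching at the injection site is an expected reaction to an adjuvanted injection. FLU-v-001 reported as many events of it as of swelling, and swelling is on the card.

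If the card does not ask, a blank in the diary tables means that the item was not prompted. It does not mean that the reaction was absent. Protocol 10.1 says that earlier trials gave a single dose only, so this trial supplies the first human description of a two-dose course. At stake is the completeness of that description, and of the secondary endpoint that carries it.

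**Working it through.** The point involves no power or sample-size figure. The check is a comparison of lists, followed by tracing each reporting route.

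**Step 1. Compare the items** (Protocol 5.2.3.1 against Protocol 12.4).

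| | Local | Systemic |
|---|---|---|
| In both trials | pain | headache, malaise, fatigue, myalgia, nausea, chills |
| FLU-v-001 only | itching, tenderness | fever, vomiting, diarrhoea, other |
| This trial only | swelling, erythema, induration, ecchymosis | arthralgia, sweating |

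Counts: FLU-v-001 has 3 + 10 = 13 entries, of which 7 are kept and 6 are not. This trial has 5 + 8 = 13, made up of the 7 kept and 6 new.

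**Step 2. Take the three terms seen only with adjuvant.** Swelling (6 events) is prompted. Pruritus (6) and pyrexia (1) are not. So 6 + 1 = 7 of 6 + 6 + 1 = 13 such events fall under terms that the present card, as described, would not prompt. These are event counts. The section does not give the number of subjects behind each term, so no rate per subject can be derived.

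**Step 3. Follow the diary route.** SAP 5.4 restricts the summary to events on the card. With neither item listed in 12.4, neither can have a row in Tables 14.2.2.11.1 or 14.2.2.11.2.

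**Step 4. Follow the other routes.**
- Protocol 13.1.7 has subjects record any symptom after dosing, to be classed as an adverse event and graded with Appendix 4.
- Protocol 15.2 provides open questions, and Table 9-2 schedules adverse event review at the second vaccination and at admission. Events captured this way appear in the 14.3.x tables.
- Table 9-2 schedules vital signs, which include temperature, on Day -43, on Day -22 and at admission. Nothing is scheduled in between that would detect a brief fever.

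**Step 5. Scope.** With up to 123 challenged subjects and two cards each, up to 123 x 2 = 246 diary periods are affected, plus those of subjects vaccinated but replaced before challenge. This counts the periods in which the items are not prompted. It does not count missed events.

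**The case against.** The strongest reply is that these reactions have another way in. Protocol 13.1.7 and 15.2 allow any symptom to be recorded as an adverse event, and the 14.3.x tables report such events by severity and relationship. In addition, 12.4 requires 60 minutes of observation after each injection. FLU-v-001 saw most of its local reactions at five minutes, mostly mild and none severe. FLU-v-002 named pain, swelling and erythema as the most common reactions in the FLU-v group, and all three are on the card. Chills, sweating and malaise may stand in for fever. Because placebo carries the adjuvant, an adjuvant reaction will not separate the arms.

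Most of this stands, and it limits the point. A reader might infer that nobody asks about fever or itching, or that the trial cannot report them at all. The documents do not support that, because the open questions and the 14.3.x tables remain. Protocol 15.2.2 keeps diary symptoms out of the individual adverse events unless clinically significant. A reader might conclude that itching written on the card by hand would vanish. That section does not address unlisted symptoms, and 13.1.7 gives them a route.

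A reader might also want vomiting and diarrhoea added. FLU-v-001 reported no vomiting and one diarrhoea event, neither tied to the adjuvant, so the same argument does not reach them.

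The reply does not supply daily prompting, and it does not put itching or fever into the diary-based endpoint. An hour of observation does not cover 21 days. Chills are an uncertain proxy: FLU-v-001 reported a pyrexia event but no chills, although a single event proves little.

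**Conclusion.** The point holds as a modest, cheap improvement in reactogenicity capture. It is confined to the diary tables and does not touch the primary efficacy analysis. Itching is the firmer half, with 6 events, adjuvanted subjects only, and a sister term with the same count that was kept. Fever rests on 1 event. The effect falls mainly on the absolute description of reactogenicity and on any increment from FLU-v over its adjuvant.

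The conclusion rests on three readings:
- The lists in 12.4 match the card. The card is not among the protocol appendices, and it may have an itching, temperature or free-text line.
- The FLU-v-001 items were prompted. Section 5.2.3.1 says assessed, not solicited.
- The unnamed adjuvant in that sentence is ISA 51, which Protocol 5.2.2 names as the one chosen for the clinical studies.

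How many reactions would be lost cannot be stated. It would need a per-subject reaction rate and the share volunteered without prompting, and the documents give neither. Comparison with FLU-v-001 item by item is not a stated objective, so its loss is an inconvenience and not a failed aim.

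**What to change.** 1. Check the card against Protocol 12.4. If it already asks about itching and fever, correct 12.4 to match.
2. If it does not, add injection-site itching, and fever or feeling feverish (with temperature if taken), to the 12.4 lists and to the card. SAP 5.4 contains no symptom list of its own, so it follows the card without a change.
3. Grade both on the existing Appendix 4 rows. The fever row is stated for oral temperature, so the card should record how temperature was taken. Feverishness without a reading should be shown separately.
4. Give both items rows in Tables 14.2.2.11.1 and 14.2.2.11.2, with subjects given the revised card as the denominator.
5. For subjects who used a card without these items, state in the SAP and the clinical study report that they were not solicited. Tabulate by arm the unsolicited reports of itching and fever within 21 days of each injection.

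The SAP refers to inoculations in the past tense and already knows how far the per-protocol and intent-to-treat sets differ. Item 5 may therefore be the only part that can still be applied here.

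The cost is a reprinted card, a wording change and one extra table. If the change comes mid-study, the new rows have a smaller denominator than the rest.
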